### Secondary outcomes

Nodule hardness over time: The change in hardness of the selected nodule for participants will also be assessed on each treatment at baseline, 3, 6, 9, 12, and 18 months after the first treatment.

Nodule size: Nodule size will be assessed using an ultrasound scan at baseline, 3, 6, 9, 12, and 18 months. Videos will also be obtained to ensure that the entire cross-section of the nodule has been recorded. For information on the translation of ultrasound images into measurement data for analysis please see **Appendix 4: Ultrasound images analysis**.

Grip strength: Measured using a Jamar meter (CE marked) at baseline, 3, 6, 9, 12, and 18 months. Previous studies of grip strength with patients with DD pre- and post-operatively have reported no significant change (Ball et al., 2013). It is anticipated that should a participant's nodule enlarge or become tender, then their grip strength might subsequently diminish.

Range of motion of the affected digit: Range of movement is the most frequently reported measure used to monitor DD progression and has demonstrated reliability, validity and sensitivity (Ball et al., 2013). Individual range of movement of finger joints will be measured using a goniometer at baseline, 3, 6, 9, 12, and 18 months post-first injection.

Michigan Hand Outcomes Questionnaire (MHQ): This is a patient-reported hand-specific measure that, unlike some other instruments, allows the user to separately score each hand at baseline, 3, 6, 9, 12, and 18 months. It contains six distinct scales that assess overall hand function, activities of daily living, pain, work performance, aesthetics, and patient satisfaction with hand function, with each scale being converted to a score ranging from 0 to 100 for reporting (see **Appendix 3**). The MHQ has been shown to have high test-retest reliability (Chung et al., 1998, Shauver & Chung, 2013) and internal consistency (Shauver & Chung, 2013), and has good construct validity depending on the condition assessed and good responsiveness (Shauver and Chung, 2013). It is a validated measure and has been shown to be sensitive to change when used to assess change in function over time in people with early DD (Broekstra, van den Heuvel, Lanting and Werker 2018) and improvement in hand function following hand surgery for established DD (Johnston et al., 2008, Herweijer et al., 2007). The MHQ was recommended following our systematic review of outcome measures for DD (Ball et al., 2013).

Patient identified activity most restricted by DD: Participants will be asked at baseline to identify the activity most restricted by DD and to rate the restriction on a scale of 1-10. At secondary co-time points (3, 6, 9, 12, and 18 months), participants will be asked to again rate the restriction of the same activity. When applied to DD, significant improvement in median scores have been reported following fasciectomy (Engstrand, Boren and Liedberg, 2009).

Progression to surgery: Only for the digit being treated at the end of follow-up (18 months post-first injection).

Injection experience: Reported by patients using an injection questionnaire which incorporates a Visual Analogue Scale of 0 (no pain) to 10 (extreme pain). Injection experience is measured after each research injection, at baseline, 3, 6 and 9 months.

Repurposing anti-TNF for treating Dupuytren's disease (funded by Health Innovation Challenge Fund, Wellcome Trust)

EudraCT Number: 2015-001780-40 and OCTRU Reference Number CTU0028

**Adverse events (injection site assessment):** The most common adverse reaction with adalimumab is injection site reactions. The injection site will be monitored for adverse events using an 'Injection Site Response Form'; the injection responses are based on injection site reactions in the prescribing literature and in clinical trials.

### Tertiary outcomes

**Euroqol EQ-5D-5L:** The EQ-5D-5L questionnaire is a preference-based instrument widely used in economic evaluation of health care technologies to assess quality of life and is the instrument preferred by the National Institute for Health and Care Excellence (NICE) to estimate utilities for the calculation of quality-adjusted life years (QALYs, National Institute for Health and Care Excellence, 2013). The responsiveness of the EQ-5D-5L instrument in early DD has not been formally evaluated, but the instrument was successfully used in a clinical trial of strengthening and stretching of the hand for people with rheumatoid arthritis (Heine et al., 2013). Moreover, recent qualitative research has shown that the main impact of DD on quality of life is on the performance of daily activities (Wilburn et al., 2013). The EQ-5D-5L includes domains on self-care and usual activities and will be able to capture improvements or deteriorations in quality of life in both treatment arms, with measurements taken at baseline, 3, 6, 9, 12, and 18 months.

**Circulating levels of adalimumab and anti-adalimumab antibodies in the blood:** 10 ml of serum will be collected post-injection to measure circulating levels of adalimumab and antibodies to adalimumab, with tertiary co-endpoints at 3 and 12 months post-first injection. Monitoring circulating levels of adalimumab will facilitate our understanding of the kinetics of drug absorption following intranodular injections and may provide further information regarding the optimal frequency of intranodular injection. Development of anti-adalimumab antibodies may be associated with reduction of efficacy.

**Table 2:** Outcome measures and assessment time-points

Outcome measure	Time-point					
	Baseline	3 months	6 months	9 months	12 months	18 months
Tonometry	*	*	*	*	*	*
Nodule size (ultrasound)	*	*	*	*	*	*
Grip strength	*	*	*	*	*	*
Range of motion	*	*	*	*	*	*
Clinical assessment of the hand	*	*	*	*	*	*
MHQ	*	*	*	*	*	*
Most restricted activity score	*	*	*	*	*	*
Injection experience	*	*	*	*		
Adverse event assessment	*	*	*	*	*	
Blood sample	*	*			*	
EQ-5D-5L	*	*	*	*	*	*

Repurposing anti-TNF for treating Dupuytren's disease (funded by Health Innovation Challenge Fund, Wellcome Trust)  
EudraCT Number: 2015-001780-40 and OCTRU Reference Number CTU0028

Outcome measure	Time-point					
	Baseline	3 months	6 months	9 months	12 months	18 months
Progression to surgery						*

## 6.2 Analysis methods: Primary outcome

The primary outcome analysis will be performed on the ITT population, comparing intervention (adalimumab) against placebo (saline, 0.9% NaCl) for all randomised participants with available nodule hardness data.

The adjusted difference in the mean change of nodule hardness between the two groups will be reported with 95% confidence intervals. The primary time point is 12 months. The primary analysis will be the comparison of change in nodule hardness between the adalimumab and saline groups using Analysis of Covariance (ANCOVA) adjusting for baseline nodule hardness, if it is normally distributed. If the data are not normally distributed, the data will be log-transformed in order to gain normality and geometric means with 95% confidence intervals reported. If data are not normally distributed after log-transformation, the non-parametric Mann-Whitney test will be used with no adjustment for baseline, and the median change with 95% confidence intervals will be reported.

As a supporting analysis, ANCOVA adjusting for baseline nodule hardness as well as the stratification factors comprising centre (Oxford, Edinburgh or Groningen) and age (as a continuous variable) will be conducted.

As a further supporting analysis, in order to analyse change in nodule hardness over the full time period, linear mixed effects regression will be used to compare nodule hardness between interventions utilising all available time-points up to 18 months and adjusting for stratification factors. Multilevel models permit all available data to be included in the analysis, thus eliminating complete case bias.

**Appendix 5: Outcome measure summaries, Table 8:** Mean (with SD) nodule hardness recorded at each study time-point.

**Appendix 5: Outcome measure summaries, Table 9:** Mean (with SD) nodule hardness at 12 months by number of injections received.

**Appendix 5: Outcome measures analysis, Table 17:** Nodule hardness ANCOVA and linear mixed-effects regression results for all follow-up time-points.

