### 3.3 Sample Size

The sample size is based on unpublished data acquired in a pilot study 'Ultrasonographic (grey scale) characteristics of DD and their relationship to the clinical features and functional severity of the disease: a pilot study' (REC Ref. 11/SC/0447). Within the study there were 25 participants with mean nodule hardness of  $53 \pm 8$  for participants suffering DD and  $32 \pm 3$  for corresponding controls matched by age and sex.

Using the study, a minimum of 138 participants (69 per arm) would be required to detect a moderate effect size of 0.62, based on a 5 point change in nodule hardness at 12 months and assuming a standard deviation of 8 (5% significance (2-sided) and 90% power, allowing for a 20% loss to follow up).

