### 3.6 Blinded analysis

A blinded analysis of data (data analysed with no treatment information added) will be undertaken prior to the final data lock in order to clarify whether continuous variables are normally distributed and to identify participants who will be excluded from the per-protocol analysis.

Primary outcome measurements were conducted using two validated portable durometers. Following identification of potential issues with the initial study device with nodule hardness recording in patients with marked distortion of the skin close to their DD nodule, a second device which would not be affected by such distortions, was sourced and utilised. Patients in two study centres (Oxford and Edinburgh) had all subsequent measurements taken using both devices and patients in one study centre (Groningen) had all of their study measurements recorded using the newer device only. During the blinded analysis the results from the two durometers will be compared using a Bland-Altman plot. A cross-walk methodology will be used to map the results from the old tonometer to the results of the new tonometer, to allow maximum data utilisation. If this cross-walk is not effective in mapping the tonometer results, alternative measures may include favouring the results from the new device and using the results from the original device only where data for the new device are not available.

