### 3.7 Statistical Analysis Outline

In the RCT (**Part 2**), all analyses will be performed on participants randomised to **Part 2** only, on an intention-to-treat basis with sensitivity analyses run on the per protocol population.

The primary outcome measure is change in nodule hardness from baseline to 12 months. There will only be one dose level used in **Part 2**, which will be 40mg of adalimumab. It is expected that all nodules will be large enough to accommodate the injection, but if not the volume of residual IMP will be recorded. The difference in the mean change of nodule hardness between the two groups will be reported with 95% confidence intervals. The comparison of change in nodule hardness between interventions will be analysed primarily using Analysis of Covariance (ANCOVA) adjusting for baseline, if it is normally distributed. As a secondary confirmatory analysis, ANCOVA adjusting for baseline nodule hardness as well as the stratification factors comprising centre (Oxford, Edinburgh or Groningen) and age (as a continuous variable) will be conducted.

If the data are not normally distributed, the data will be log-transformed in order to gain normality and geometric means with 95% confidence intervals will be reported. If data are not normally distributed after log-transformation, the non-parametric Mann Whitney test will be used with no adjustment for baseline, and the median change with 95% confidence intervals will be reported.

In order to analyse change in nodule hardness over the full time period, linear mixed effects regression will be used to compare nodule hardness between interventions utilising all time-points up to 18 months and adjusting for stratification and other important prognostic factors.

The secondary outcome measures for **Part 2** include those for **Part 1** and also grip strength, range of motion and participant reported outcomes.

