## 6. ANALYSIS

### 6.1 Outcome Definitions

#### Primary outcome

Nodule hardness from baseline to 12 months: The primary outcome is hardness of nodule selected for treatment measured at 12 months post-first injection using a validated portable durometer. During the initial stages of this study researchers within the team noted that the original portable durometer being used to measure nodule hardness in the UK-based centres was potentially unable to achieve accurate measurements in patients with moderate to severe deformities of their hands due to their DD. Following this an alternative durometer with a longer probe, which would be able to overcome this issue, was sourced. To ensure patients who had nodule hardness data collected using only the original durometer were not excluded from analyses, or included with inaccurate data, all subsequent patients recruited in the UK-based centres had their nodule hardness data collected with both the original and the new portable durometer. The centre in the Netherlands only recorded data using the newer portable durometer.

The outcomes for RIDD were tested in our ultrasound study (REC Ref. 11/SC/0047) 'Ultrasonographic (grey scale) characteristics of DD and their relationship to the clinical features and functional severity of the disease: a pilot study'. Preliminary (unpublished) tonometry data from 25 patients in this trial demonstrated that the

Repurposing anti-TNF for treating Dupuytren's disease (funded by Health Innovation Challenge Fund, Wellcome Trust)

EudraCT Number: 2015-001780-40 and OCTRU Reference Number CTU0028

palmar tissue of patients with untreated DD were significantly firmer than the corresponding age and sex matched controls.

Using the measurements from the portable durometers, the amount of indentation is converted to hardness reading on a scale with 100 units (internationally standardised durometer units). The time window for collecting the primary end-point nodule hardness data will allow  $\pm$  4 weeks to confer some flexibility. This will be extended to  $\pm$  3 months where physical measurements could not be safely recorded due to the SARS-CoV-2 pandemic.

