### 6.2.1 Missing data

The number and proportion of individuals in the missing category will be presented, as well as reasons for missing if known. It is anticipated that there will not be a high level of missing data for the primary outcome since the blinded assessor will measure nodule hardness at each follow-up visit attended by participants. However, data could be missing if a patient withdraws or does not attend for clinical assessment.

Missing data distributions will be explored to assess whether the assumption that data are missing at random (MAR) – a core assumption under which principal analyses will be conducted – is true. If MAR can be demonstrated, multiple imputation using chained equations (MICE) will be used to impute missing data. The use of MICE in place of more simple imputation techniques allows for variability in patients disease starting point and progression to be accounted for within the imputed dataset, across all time-points. The impact of

Repurposing anti-TNF for treating Dupuytren's disease (funded by Health Innovation Challenge Fund, Wellcome Trust)

EudraCT Number: 2015-001780-40 and OCTRU Reference Number CTU0028

missing primary outcome data on modelled treatment effect will be assessed under a range of assumptions about the missing data, in which the data and missingness will be modelled jointly using a pattern-mixture model (PMM; White et al., 2018), which assesses the sensitivity of the analysis result to departures from a missing at random assumption. Sensitivity analyses, including PMM, will be run on the non-imputed ITT dataset, the non-imputed per protocol dataset and on the MICE imputed dataset to explore the missing data assumptions (see **6.2.1 – Sensitivity analysis**). Methods for handling missing data will be finalised during the blinded analysis, before the final analysis data-lock.

During the analysis, techniques other than those suggested above may be used, for instance if data are not normally distributed or in the case of new techniques being developed in the meantime. No data will be considered spurious in the analysis since all data will be checked and cleaned before analysis.

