## 20. OUTCOME MEASURES ANALYSIS

### 20.1 Primary outcome

**Table 19:** Nodule hardness ANCOVA and linear mixed-effects regression results for all follow-up time-points

	Saline			Adalimumab			Treatment effect			
	N =	n	Mean change	N =	n	Mean change	SD	Mean difference	95% confidence interval	P-value
ANCOVA a										
12 months										
Adjusted ANCOVA b										
12 months										
Mixed effects regression b										
Baseline										
3 months										
6 months										

Repurposing anti-TNF for treating Dupuytren's disease (funded by Health Innovation Challenge Fund, Wellcome Trust)  
EudraCT Number: 2015-001780-40 and OCTRU Reference Number CTU0028

	Saline N =			Adalimumab N =			Treatment effect N =		
	n	Mean change	SD	n	Mean change	SD	Mean difference	95% confidence interval	P-value
12 months c									
18 months									

a nodule hardness and treatment arm | b nodule hardness, treatment arm, age group and centre | c primary endpoint

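### The non-normality fallback for the primary outcome has no workable log step, ends in a test without baseline adjustment, and is triggered by the variable rather than the ANCOVA residuals

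*SAP*

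**What the plan says.** SAP 3.7 states: "The primary outcome measure is change in nodule hardness from baseline to 12 months". SAP 6.2 and Protocol 11.2 (Part 2) analyse the same variable by ANCOVA adjusted for baseline hardness, on condition that it is normally distributed. SAP 6.2 then gives two fallback steps, with matching text in SAP 3.7 and Protocol 11.2:

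- Step 1: "If the data are not normally distributed, the data will be log-transformed in order to gain normality and geometric means" are reported with 95% confidence intervals.
- Step 2, if normality is still not reached: "the non-parametric Mann-Whitney test will be used with no adjustment for baseline, and the median change with 95% confidence intervals will be reported".

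Four other places bear on how this rule works:

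- SAP 6.1 words the outcome as a level, not a change: "The primary outcome is hardness of nodule selected for treatment measured at 12 months post-first injection using a validated portable durometer".
- SAP 3.6 sets the trigger. A blinded look before data lock is made "in order to clarify whether continuous variables are normally distributed". Residuals are not mentioned, and no test or threshold is named.
- SAP 6.2.1 adds that "techniques other than those suggested above may be used, for instance if data are not normally distributed", without naming any.
- The primary results shell in SAP Appendix 5 (Table 19 there, cited as Table 17 in SAP 6.2), titled "Nodule hardness ANCOVA and linear mixed-effects regression results for all follow-up time-points", has columns for mean change, mean difference, confidence interval and p-value only.

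**The concern.** This rule decides which analysis is the confirmatory one, so each step must be computable and must answer the question the trial was sized for. There are three difficulties.

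1. **Log step.** The named variable is a change, which can be zero or negative. No offset, no other scale and no rule for such values is given.
2. **Last step.** SAP 6.2 opens by promising an adjusted difference in mean change. It ends with an unadjusted rank test and a median change that is not defined as a between-group contrast.
3. **Trigger.** ANCOVA rests on the distribution of its residuals. The check is on the variable, and without treatment codes the residuals of the treatment model cannot be formed. The wording is also looser than for secondary outcomes, where SAP 3.7 and 6.3 act only on severe departures and tolerate near-normality.

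The shape of one variable could therefore move the primary result from an adjusted mean difference to a ratio, or to an unadjusted rank comparison.

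**Working it through.** **Inputs.** SAP 3.3 and Protocol 11.3: the size is "based on a 5 point change in nodule hardness at 12 months and assuming a standard deviation of 8", with two-sided 5%, 90% power, 20% loss and a pilot mean of 53. The baseline-to-12-month correlation r is not in the documents; 0.2 to 0.6 is assumed unless stated otherwise.

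**1. The plan's own figure.** 5/8 = 0.625. A two-sample t-test needs 54.8, so 55 per arm (power 90.1%). 55/0.8 = 68.75, so 69 per arm and 138 in total. The stated size reproduces and is not in dispute.

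**2. Share of changes that cannot be logged.** P(change ≤ 0) = Φ(−mean/SD of change), taking change as normal. The SD of 8 comes from single pilot readings. If it is that, SD of change = 8√(2(1−r)), which is 10.12 at r = 0.2 and 7.16 at r = 0.6. If it is the SD of change, use 8 directly.

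| Arm mean change (assumed) | SD of change 8 | SD 10.12 (r = 0.2) | SD 7.16 (r = 0.6) |
|---|---|---|---|
| −5 | 73% | 69% | 76% |
| 0 | 50% | 50% | 50% |
| +5 | 27% | 31% | 24% |

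**3. If hardness itself is logged.** A 5-point fall from 53 is 48/53 = 0.91; from 45 (one SD below) it is 40/45 = 0.89; from 61 (one SD above) it is 56/61 = 0.92. A constant difference is not a constant ratio, so this is a different effect measure.

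**4. Is the fallback needed for validity?** Coverage of the ordinary ANCOVA 95% interval, 55 per arm, r = 0.5, SD 8, 20,000 runs per error type:

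| Residuals | Coverage |
|---|---|
| Normal | 94.9% |
| t (4 df) | 95.0% |
| Laplace | 95.1% |
| Gamma (shape 2) | 95.0% |
| Exponential | 95.2% |
| Lognormal (σ = 0.75) | 95.3% |

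**5. What dropping baseline costs.** The variance of an unadjusted change comparison relative to ANCOVA is 2σ²(1−r) / σ²(1−r²) = 2/(1+r): 1.54 at r = 0.3, 1.33 at 0.5 and 1.18 at 0.7. Simulated Mann-Whitney power for a 5-point difference (20,000 runs):

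| Normal change scores | r = 0.2 | 0.3 | 0.4 | 0.5 | 0.6 |
|---|---|---|---|---|---|
| 55 per arm | 70.9% | 76.3% | 82.6% | 89.0% | 94.2% |
| 80 per arm | 85.9% | 90.0% | 93.8% | 96.9% | 99.1% |

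The 80-per-arm row is what 200 recruits, the protocol maximum, would leave after 20% loss. With t4, Laplace or gamma change scores at 55 per arm, power runs from about 86% (r = 0.2) to 99% (r = 0.6). If 8 is already the SD of change, it is about 89%. For comparison, ANCOVA at 55 per arm with normal errors gives 92.7% at r = 0.3 and 95.9% at r = 0.5 (4,000 runs).

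**6. The trigger.** With an assumed skewed (gamma) baseline, exactly normal ANCOVA errors, r = 0.5 and 69 per arm, Shapiro-Wilk at 5% rejected normality of the change in 11.8% of 2,000 trials and of the residuals in 5.2%. The SAP names no test, so this only illustrates that a check on the variable can set aside a sound ANCOVA.

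**The case against.** The strongest reply has five parts.

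- **Blinding.** The check uses no treatment information and precedes data lock, so the branch cannot be chosen to favour a result. That stands. It limits bias, but it neither defines the log step nor restores baseline.
- **Logging hardness.** SAP 6.1 words the outcome as hardness at 12 months on a 100-unit scale, and geometric means make sense only for positive values, so the authors may have meant to log hardness. That is plausible but unstated, and it would still replace a difference with a ratio.
- **Normality in the figures.** The unloggable shares and the lowest power figures assume normal changes, in which case the fallback would not be reached. This is fair: the shares show the order of the problem, not a forecast. Any distribution of change that straddles zero meets the same obstacle.
- **Efficiency.** Mann-Whitney can match or beat ANCOVA. With non-normal residuals at r = 0.5, ANCOVA against Mann-Whitney was 96.0 v 94.0% (t4), 95.5 v 95.9% (exponential) and 94.5 v 97.1% (lognormal), 6,000 runs each. At r = 0.2 ANCOVA was clearly better, about 90% to 91% against 75% to 82%. This stands, and it is why no power loss is claimed as shown.
- **Supporting analyses.** The ANCOVA adjusted for baseline, centre and age, and the mixed model, are not conditional on normality. A baseline-adjusted mean difference would be reported in any case, but not as the primary result.

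Nothing in the documents suggests that hardness is in fact non-normal; the defect lies in a contingent branch.

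**Conclusion.** The concern holds and should be fixed. On the natural reading, the log step cannot be computed for about a quarter to three quarters of an arm, for assumed arm mean changes of +5 to −5 and roughly normal changes. On the other reading it is unstated and changes the effect measure. The final step can always be computed, so a result will exist, but it discards a baseline the trial collects and swaps the adjusted mean difference for a median change that the results shell has no column for. The trigger examines the wrong quantity. The clause allowing other techniques names none and so repairs nothing.

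The switch is not needed for valid inference at this sample size: ANCOVA coverage stays within 94.9% to 95.3% under the residual shapes tried (r = 0.5, equal variances). Whether power would fall below 90% depends on r and on whether 8 is the SD of a reading or of a change, and the documents settle neither. ANCOVA remains the default, which is why this is a matter to correct and not a fatal flaw.

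**What to change.** In SAP 3.7 and 6.2 and Protocol 11.2 (Part 2):

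- Keep baseline-adjusted ANCOVA of 12-month hardness as the primary analysis whatever the marginal distribution. It gives the same treatment effect as ANCOVA of change.
- Check the residuals. If they are clearly non-normal or heteroscedastic, keep the same estimate and use robust or bootstrap confidence intervals.
- Move any rank-based analysis to sensitivity, as a baseline-adjusted rank ANCOVA. It uses the baseline already collected, and it had higher power than Mann-Whitney in all 12 simulated scenarios.
- If a log analysis is wanted, define it as log 12-month hardness adjusted for log baseline, reported as a ratio of geometric means, also as sensitivity.

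The cost is wording before data lock, with the review and sign-off that Protocol 11.7 requires and a protocol amendment where appropriate. Time is short: SAP 3.1 expects the final analysis to start on 26 January 2021, 19 days after SAP version 2.0. No new data are needed, the sample size is unchanged, and the existing primary results shell then fits as it is.
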